4. SUMMARY

Reducing unintended pregnancy is a national and global priority, and improving women's choice of contraception is a vital step. There are many myths, misunderstandings and concerns about contraception, and increasingly women turn to online resources for information on healthcare.

The aim of the study is to develop and test the feasibility of an online trial of a website to increase the acceptability, uptake and adherence to long-acting reversible contraceptive (LARC) methods in young women. LARC methods include the intrauterine device (IUD), intrauterine system (IUS), subdermal implant (SDI) and depo injection.

In Phase 1 of this study (completed) we developed a self-guided website that presents recommended contraceptive options in response to women's preferences. The website will be presented on a touch-screen tablet computer in clinic waiting areas or pharmacy consulting areas.

In Phase 2 (this study), we will assess feasibility of an online trial of the contraception choice website in five sites:

An NHS sexual health service (Margaret Pyke Centre, MPC)

A local general practice

A maternity service (Ashford & St Peter's Hospitals NHS Foundation Trust)

A community pharmacy (Greenlight)

An abortion service (bpas)

Phase Two will take 15 months including:

- Conducting a randomised pilot trial across the five settings
- Conducting a qualitative process evaluation of the website, of NHS implementation issues and of research procedures
- Analysis, reporting and dissemination of study findings
- Preparation of outputs, including a protocol for a definitive RCT to increase uptake and adherence of LARC that is informed by both quantitative and qualitative findings In each setting we will recruit 80 women aged 15-30 years (40 randomised to intervention and 40 to control) and follow them up by online questionnaire at 3 and 6 months (or 2 months after delivery for post-partum women).
- *Funder-approved amendment to recruitment*. In addition to the above, we will recruit 530 more women from one site only, the Margaret Pyke Centre, via their Central (telephone) Booking System. Women requesting an appointment for

contraception will be invited to go online and enter the trial before they attend their appointment.

Data collection:

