- Provider views about impacts on the service and trial procedures, assessed through qualitative interviews with 15 key staff in total (3 per site), sampling those who have roles in facilitating the study in each setting (e.g. receptionists, practice managers, nurses, midwives, doctors and pharmacists) (see Topic Guide). Questions to be explored include:
 - Are recruitment procedures acceptable to staff?
 - How might recruitment procedures be improved, to optimise recruitment to a fullscale trial?
 - What are staff views on the feasibility and usefulness of a contraception decision website in each clinic setting?

9. SAMPLE SIZE and RECRUITMENT

The original target sample size of 80 participants in each of the five settings was based on estimating an expected follow-up rate at 6 months of 70% to within 10% precision (95% Cl 60% to 80%) for each setting. This sample size also provided 80% power to detect a significant difference (at the 5% level) in the follow-up rate between two settings if the true difference is 22% (e.g. 59% vs. 81%). By pooling data across settings this sample size also provides 80% power to detect a significant difference (at the 5% level) in the follow-up rate between the follow-up rate between the intervention and standard arms if the true difference is 15% (e.g. 62.5% vs. 77.5%). The expected follow-up rate is based on a previous sexual health study that recruited and followed-up the participants online (Sex Unzipped).

Funder-approved amendment to sample size:

A further 530 participants are to be recruited from one existing site, though recruited in a different way (from the central booking system). Together with the original target size this

leads to a total of 930 participants. This new total sample size is calculated to provide power to assess the effect of the intervention on the revised primary outcome which is uptake of LARC at follow-up. Specifically, assuming a follow-up rate of 70%, this sample size provides at 82% power to detect as significant (at the 5% level) an increase from 35% (control group prevalence) to 47% in LARC use due to the intervention.

The recruitment period of 6 months is based on:

- the volume of patients attending each of the study sites, which is high i.e. hundreds or dozens of women per week in four sites GP, SRH, maternity service and bpasand at least 30 women per month in the pharmacy,

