Participants will then be asked to give their contact details (email address, telephone number, and postal address), in order to contact them for follow up assessments, to send the intervention group reminders to view the website, and to remind them that they are participating in the trial, and to send an electronic voucher to recompense participants for their time. Participants will be given the option not to give some of this information; however an email address is compulsory, to contact them for follow-up assessments. Participants who decline to give an email address will be excluded from the study.

^a This information will be completely anonymous, as participants will not be asked to give any personally identifying details. This data will only be stored for information regarding recruitment and exclusion ^b if they choose to participate, this will be sent to them via email for future reference

Demographic and baseline sexual health data will then be collected (see '*Measures*'). Participants will be given the option to withdraw from the study at any time after giving consent. All follow-up emails that participants receive will include a link to allow them to withdraw from the study, including one which will be sent to them immediately after registration.

Funder-approved amendment to recruitment

In addition to the recruitment above, we will recruit an additional 530 women from one site only, the Margaret Pyke Centre, via their Central online Booking System. Currently, when women request an appointment for contraception, they are directed to the Trust website to book their appointment. For this study, women will be informed on the Trust website that the clinic is taking part in a study to improve information about contraception, and inviting them to go online (by clicking on a hyperlink) and see if they want to take part in the study before they attend their appointment. Clicking on the hyperlink will take women to the trial website from where all procedures are the same as above.

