The primary outcome of LARC use at 6 months will be analysed among women in need of contraception (not pregnant or currently trying to become pregnant) and the primary outcome of satisfaction with method will be analysed among women who are using a method at 6 months. The primary outcome of LARC use at 6 months will be analysed stratified by LARC use at baseline, leading to three intervention effects: the effect in baseline LARC users, the effect in baseline non-users, and the overall effect adjusted for baseline LARC use. In the event that over 90% of baseline LARC users in the control arm are using a LARC method at 6 months (or no longer need contraception) then the primary effect measure for this outcome will be the intervention effect in non-LARC users. If conversely fewer than 90% of baseline LARC users in the control arm are using a LARC method at 6 months then the primary effect measure will be the overall adjusted intervention effect. A further subgroup analysis will be conducted for both primary outcomes to assess, based on testing an interaction term, whether the effect of the intervention varies by setting.

Primary comparisons between arms will be based on multiple imputation where outcomes at 6 months are imputed based on outcomes at 3 months for those participants who completed the 3 month outcome questionnaire but failed to complete the questionnaire at 6 months.

Health Economics

The primary analysis will be a budget impact analysis of the website and contraception reporting the total costs to each payer (NHS (primary care versus secondary care), local government, private and out of pocket). This will reported as total cost of contraception and pregnancy outcomes for a range of different population sizes. The analysis will conform to the ISPOR good practice guidelines for budget impact analysis.²¹

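### The 82% power stated for the LARC primary outcome does not follow from its own inputs, which give about 88%; the between-arm follow-up power is also understated

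*Protocol*

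**What the plan says.** Section 9 adds 530 women to the 400 first planned, which "leads to a total of 930 participants". It powers this total for LARC use at follow-up, "assuming a follow-up rate of 70"%, and concludes that "this sample size provides at 82% power to detect as significant (at the 5% level) an increase from 35% (control group prevalence) to 47"%.

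The same section makes two power statements about follow-up rates for the 80-per-setting target:

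- Between settings: "80% power to detect a significant difference (at the 5% level) in the follow-up rate between two settings if the true difference is 22"%, with 59% versus 81% as the example.
- Between arms, pooling the settings: again 80% power, "if the true difference is 15% (e.g. 62.5% vs. 77.5"%).

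The Summary gives the allocation within each setting as "40 randomised to intervention and 40 to control". For the added women section 10.3 says "Clicking on the hyperlink will take women to the trial website from where all procedures are the same as above", so no other ratio is stated. Section 10 describes individual randomisation in parallel groups. No design effect or multiplicity adjustment appears.

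Section 10.5 restricts the LARC analysis to women in need of contraception. It adds that if more than 90% of control-arm baseline LARC users are still using LARC or no longer need contraception, "then the primary effect measure for this outcome will be the intervention effect in non-LARC users".

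**The concern.** The sentence in section 9 is the only power statement for LARC use as a primary outcome, and it is the stated reason for going from 400 to 930 women. All its inputs are given apart from the sidedness of the test, so it should reproduce. It does not, which means that an input is misreported, an allowance is undisclosed, or the power is simply wrong. A reader cannot tell which. Objective 7 is to write the protocol of a definitive trial, and the error could be carried into that calculation.

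The statement also counts every followed woman, whereas section 10.5 analyses a subset.

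**Working it through.** **Inputs.** Total 930, follow-up 70%, 5% level, 35% and 47% (section 9). Allocation is 1:1 (Summary; assumed for the added 530). The test is taken as two-sided, which is an assumption.

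Followed women: 930 × 0.70 = 651, or 325.5 per arm.

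**Formula.** With n per arm, d = p2 − p1 and p̄ the mean of p1 and p2,

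power = Φ{ [d√n − 1.960 √(2p̄(1 − p̄))] / √(p1(1 − p1) + p2(1 − p2)) }.

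For the continuity correction, replace n by (n − 1/d)²/n.

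**1. The stated comparison, 35% versus 47%.**

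- d√n = 0.12 × √325.5 = 2.165
- √(2 × 0.41 × 0.59) = 0.6956
- √(0.35 × 0.65 + 0.47 × 0.53) = 0.6904
- (2.165 − 1.960 × 0.6956)/0.6904 = 1.161, so power = 87.7%

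| Method | Power |
|---|---|
| Pooled variance | 87.7% |
| Unpooled variance | 88.0% |
| Arcsine | 87.7% |
| Continuity-corrected (n becomes 309.05) | 86.0% |
| Fisher's exact test (325 per arm) | 86.1% |
| One-sided 5% | 93.0% |
| No loss to follow-up (465 per arm) | 96.2% |

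The nearest is 4 points above 82%. For 35% versus 47%, 82% power needs only 277 followed per arm, that is 2 × 277/0.70, about 792 randomised. This is 138 fewer than 930.

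**2. What would give 82%.**

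| Change to one input | Power | Position in the protocol |
|---|---|---|
| 35% versus 46% | 81.7% | not stated |
| 36% versus 47% | 81.4% | not stated |
| 60% follow-up (279 per arm) | 82.3% | section 9 says 70% |
| Two-sided 2.5% level | 81.0% | section 9 says 5% |
| 2:1 allocation | 83.6% | Summary gives 40 and 40 |
| Design effect 325.5/277 = 1.18 | 82% | not stated |

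**3. Restriction to women in need of contraception.** The protocol gives no figure for those excluded, so a range is assumed, keeping 35% versus 47%.

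| Excluded | n per arm | Power |
|---|---|---|
| 5% | 325.5 × 0.95 = 309 | 86% |
| 10% | 325.5 × 0.90 = 293 | 84% |
| 15% | 325.5 × 0.85 = 277 | 82% |

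**4. Follow-up rate between arms, 62.5% versus 77.5%.** Five settings of 80 give 400 women, 200 per arm. Follow-up is observed for everyone randomised, so there is no attrition to allow for.

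- d√n = 0.15 × √200 = 2.121
- √(2 × 0.70 × 0.30) = 0.6481
- √(0.625 × 0.375 + 0.775 × 0.225) = 0.6393
- (2.121 − 1.960 × 0.6481)/0.6393 = 1.331, so power = 90.8%

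The continuity-corrected figure is 88.9% and Fisher's is 89.1%. Power of 80% for this difference needs 146 per arm (159 corrected). With 200 per arm, 13 points (63.5% versus 76.5%) has 81.2% power. With the correction, 13 points has 78.1% and 14 points (63% versus 77%) has 84.1%.

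**5. Follow-up rate between settings, 59% versus 81% with 80 each.** Power is 86.6% uncorrected, 82.4% corrected and 82.9% by Fisher's test. With the correction, 21 points (59.5% versus 80.5%) has 78.4%.

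**The case against.** **The error is on the safe side.** On the stated inputs the trial has more power than claimed, and no recruitment target, analysis or conclusion changes. This stands and limits the weight of the point. It does not make the figure right.

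**The sentence is garbled.** It reads as though a word is missing before 82%. If that word were *least*, the claim would be literally true. The text cannot settle this, and quoting a floor 6 points below the actual power would still need explaining.

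**Gains as well as losses.** Section 10.5 includes anyone with at least one follow-up questionnaire and imputes 6-month outcomes from 3 months. If 70% is the 6-month rate, the number analysed could exceed 651. This is fair, so the 82% to 86% range in step 3 is illustrative.

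**Stronger readings that a reader might infer, and that the documents do not support:**

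- *That 46% was the intended rate.* It is the simplest repair, but step 2 shows several others. The protocol does not say which applies.
- *That power drops to 74–78% if baseline non-users become the primary group.* This comes from applying 35% versus 47% to the 247 or 228 per arm left after removing 24% or 30% as baseline users (the clinic figures in section 6, not trial data). But section 9 gives 35% as the prevalence in the whole control arm, baseline users included. With 90% of those users continuing, the non-user control rate would be (0.35 − 0.9 × 0.24)/0.76 = 17.6%, or (0.35 − 0.9 × 0.30)/0.70 = 11.4%, and lower still with higher continuation. A 12-point rise from those rates has about 88% and 92% power. No shortfall is shown.
- *That the 22-point between-setting statement is also wrong.* With continuity correction, 22 points is the smallest whole-point difference that reaches 80% (step 5). It is defensible.

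**Conclusion.** The concern holds for two statements in section 9. The primary power is about 88% (86% corrected or exact) where 82% is stated. The between-arm follow-up power is about 91% (89% corrected or exact) where 80% is stated. Both results assume a two-sided 5% test and 1:1 allocation; the first also takes the 651 followed women as the number analysed.

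Both errors understate power, so they are not evidence that the trial is too small. The first matters more because it concerns a primary outcome and is the stated ground for the sample-size amendment. The second concerns follow-up rate, which is now a secondary outcome.

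That section 9 makes no allowance for women not in need of contraception is a gap in the description. At assumed exclusions of 5% to 15%, power remains at or above about 82%.

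**What to change.** In section 9:

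1. Restate the primary power as about 88% for 35% versus 47% with 651 followed women, two-sided 5%, 1:1. Alternatively, state the input that was actually used (for example 35% versus 46% at 82%). The sponsor has to say which.
2. Note that the figure counts all followed women whereas section 10.5 analyses those in need of contraception, and give the power under an explicit assumption for the proportion excluded.
3. Restate the between-arm follow-up power as about 91% for 62.5% versus 77.5% with 200 per arm, or give the difference detectable with 80% power as about 13 points (14 with continuity correction). Name the method used.

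The between-setting statement can stay. These are wording changes only; recruitment and analysis are unaffected.

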- the proportion of women invited to take part in the study who accept which, given the financial incentives to take part, is expected to range from 20% to 30%.

Category	Name	Details
Sexual and Reproductive	Margaret Pyke Centre	[name]
Health Service		[name]
Abortion Service	British Pregnancy Advisory	BPAS London East. [name]
	Service	[name]
		[name].
Community Pharmacy	Green Light Pharmacy	[name]
	Shepherd's Bush	[name]
Maternity Service	Ashford & St Peter's	St Peter's Hospital,
	Hospitals NHS Foundation	[name]
	Trust	[name]
General Practice	General Practice in Camden	Clerkenwell Medical Practice
	and Islington	[name]
		[name] (to
		be confirmed)

Sites

These five clinical settings were chosen because, together, they provide contraceptive care for the great majority of women in the UK. In addition, they include services that provide care for women at highest risk of unintended pregnancy (i.e. those who attend abortion services or seek emergency contraception through community pharmacies). Development of interventions that are feasible and acceptable to women and providers in these settings therefore has the greatest potential for impact.

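### The stated basis for the 6-month recruitment period supports about 36 to 54 women at the pharmacy, not the 80 on which the per-setting precision and power rest

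*Protocol*

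**What the plan says.** Protocol section 9 (Sample size and recruitment) starts from "The original target sample size of 80 participants in each of the five settings". It ties that number to an "expected follow-up rate at 6 months of 70% to within 10% precision (95% Cl 60% to 80%) for each setting", and says it also gives "80% power to detect a significant difference (at the 5% level) in the follow-up rate between two settings" when the true rates are, for example, 59% and 81%. The Summary (section 4) likewise commits to 80 women in each setting.

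Section 9 then explains the timescale: "The recruitment period of 6 months is based on" two inputs. The first is patient volume. Four sites are described as seeing dozens or hundreds of women a week, while the pharmacy is put at "at least 30 women per month in the pharmacy". The second is the share of invited women who agree, which "is expected to range from 20% to 30" per cent.

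Other sections bear on the point:
- Section 8 lists recruitment rate as a secondary outcome, measured as the time to recruit up to 80 women per site.
- Section 10.5 reports recruitment and follow-up rates by setting.
- Section 18 places recruitment between January and July 2017.

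The protocol gives no higher pharmacy volume, no longer window for that site and no fallback.

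**The concern.** The two inputs offered as the reason why 6 months is enough do not lead to 80 women at the pharmacy. The gap is specific to that site, because the other four have volumes of a different order.

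Two things are at stake. First, the precision and between-setting power in section 9 are claimed for every setting, and at the pharmacy they depend on a number that the plan's own figures do not reach. Second, recruitment rate and comparative ease of implementation across settings are feasibility measures of this pilot (sections 4 and 8). If the pharmacy is judged against 80 in 6 months, a shortfall that the planning figures already imply could be reported as a discovery about pharmacies.

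**Working it through.** **Inputs (protocol section 9 unless noted).** Target 80 per setting; period 6 months; pharmacy volume 30 women a month (a minimum); acceptance 20% to 30%; expected follow-up 70%; between-setting contrast 59% versus 81%; 5% level, taken as two-sided because the protocol does not say. As a sensitivity case, January to July 2017 (section 18) is read as 7 months.

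**Step 1: reproduce the plan's figures at 80.**
- Half-width of the 95% interval = 1.96 x sqrt(0.7 x 0.3 / n). At n = 80 this is 10.04 points, so the stated ±10 reproduces.
- Power for 59% versus 81%, 80 against 80: 86.6% by the uncorrected normal approximation, 82.4% with continuity correction, 82.9% by Fisher's exact test. The stated 80% is met.

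**Step 2: pharmacy yield = women per month x months x acceptance.**
- 6 months: 30 x 6 = 180 women; 180 x 0.20 = 36; 180 x 0.30 = 54. That is 45% to 68% of 80.
- 7 months: 210 x 0.20 = 42; 210 x 0.30 = 63.

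This is generous, since it treats every woman counted in the volume as eligible and invited.

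**Step 3: what 80 would require.**
- Acceptance at 30 a month for 6 months: 80 / 180 = 44%, against a planned maximum of 30%.
- Volume in 6 months: 80 / (6 x 0.30) = 44.4 a month, up to 80 / (6 x 0.20) = 66.7 a month. This is 48% to 122% above the stated minimum.
- Time at 30 a month: 80 / (30 x 0.30) = 8.9 months, up to 80 / (30 x 0.20) = 13.3 months.

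**Step 4: precision at the implied yield.**
- n = 54: 1.96 x sqrt(0.21 / 54) = 12.2 points.
- n = 36: 1.96 x sqrt(0.21 / 36) = 15.0 points.
- 7-month reading, n = 63 and 42: 11.3 and 13.9 points.

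**Step 5: power for 59% versus 81%, pharmacy against a setting of 80.** With n1 the pharmacy number, k = 80 / n1, p1 and p2 the two rates and p their weighted mean (p1 + k p2) / (1 + k), uncorrected power is Φ{[0.22 sqrt(n1) − 1.96 sqrt(p(1 − p)(1 + 1/k))] / sqrt(p1(1 − p1) + p2(1 − p2)/k)}. Ranges cover which of the two settings has the lower rate.

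| Pharmacy n | Uncorrected | Continuity-corrected | Fisher exact |
|---|---|---|---|
| 36 | 65–70% | 56–62% | 63–66% |
| 54 | 78–79% | 71–73% | 76% |

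At 63 women (7 months, 30% acceptance) uncorrected power is about 82%, which meets the stated 80%.

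**Step 6: pooled comparisons with the pharmacy at 36 to 54 (uncorrected).**
- Follow-up by arm, 62.5% versus 77.5%: the total becomes 320 + 36 = 356 to 320 + 54 = 374, and power is 87% to 89%, against a stated 80%.
- LARC use, 35% versus 47%, 70% follow-up: the total becomes 930 − 44 = 886 to 930 − 26 = 904, leaving about 620 to 632 followed up. Power is 86.1% to 86.8%, compared with 87.7% at 930 and a stated 82%.

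**The case against.** The strongest reply is that 30 a month is a minimum. The range 36 to 54 is therefore the yield at the lowest footfall, not a forecast. This stands. A reader might infer that the pharmacy cannot recruit 80 women; the protocol does not support that, because actual volume may be higher. What remains is that the minimum is the only pharmacy volume offered to justify the period, and it would have to be exceeded by about half to more than double.

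A second reply is that section 8 words the target as up to 80 and makes time to recruit an outcome, so slow recruitment at a site is something the pilot means to measure. That softens the point. It does not remove the conflict, because section 9 still claims its precision for each setting on the basis of 80.

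Third, the per-setting claims belong to the original target, and follow-up rate is now secondary. This limits the consequence. A reader might also infer that a pharmacy shortfall endangers the total of 930 and with it the LARC comparison. Step 6 shows otherwise: losing 26 to 44 women costs less than two points of power and leaves it above the stated figure.

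Finally, the power loss is small at the favourable end: one to two points below 80% at 54 women without correction, and none at 63. This is correct. The loss of precision persists throughout, at ±11.3 points even with 63 women.

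**Conclusion.** The point holds as an inconsistency at one of the five sites. On the stated minimum volume and acceptance range, 6 months yields 36 to 54 pharmacy women against a target of 80, and 7 months still falls short. The pharmacy's follow-up rate would then be estimated to about ±12 to ±15 points. Between-setting power against a setting of 80 would be about 65% to 79% uncorrected, and lower with a continuity correction. The precision shortfall is clear across the range; the power shortfall is clear at the low end and slight at the top.

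These figures assume footfall at the stated minimum, every woman eligible and invited, 70% follow-up and a two-sided 5% test. Higher footfall would narrow or close the gap. The damage is confined to pharmacy-specific estimates, pairwise contrasts with the pharmacy and the interpretation of its recruitment rate.

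**What to change.** Amend section 9 in one of two ways.

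1. If the expected (not minimum) pharmacy volume supports 80 women in the recruitment period, state it. At 20% to 30% acceptance over 6 months that means about 67 down to 45 women a month.
2. Otherwise, state that the pharmacy is expected to yield about 36 to 54 women, with 80 kept as the ceiling in line with section 8. Restate its precision as about ±12 to ±15 points, and give the between-setting power for contrasts that involve it, naming the test. Say that its recruitment rate will be judged against the expected yield.

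Either is a change of wording. The first needs a footfall figure from the site; the second costs a less favourable precision and power statement for one setting. Keeping the minimum volume and extending the pharmacy's window to 9 to 13.3 months would be costly within a 15-month Phase 2. Making up the numbers from the booking-system stream is not needed for the LARC comparison and would restore nothing about the pharmacy.
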